**The sample size of this study will not exceed 24 patients.**

11.3.3 There will be an early stopping rule for unexpected toxicity. If at any point during the study more than 1/6 of patients treated to date experience study treatment-related grade 4-5 toxicity of any kind, study enrollment will be suspended. Treatment related events include those related or possibly related to therapy.

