## **STUDY SYNOPSIS**

### **Interstitial Radioactive Iodine Implants for the Treatment of Pituitary Macroadenomas**

#### Schema

#### **Patient Population:** (See Section 3.0 for Eligibility)

Patients must have biopsy proven pan-invasive pituitary macroadenomas of the pituitary gland. Pan-invasive for the purposes of the protocol will be defined as meeting each of the following 2 major criteria:

1. tumor volume greater than 20 cc at enrollment, and
2. suprasellar extension.

In addition, a pan-invasive tumor must meet any one of the following 3 minor criteria:

- a) unresectable tumor invasion into a cavernous sinus,
- b) bone or bone marrow invasion into the clivus or temporal bones, or
- c) tumor extension in any direction unlikely to be completely removed specifically by a transphenoidal surgical approach.

Patients who meet the two major criteria above (1 and 2) and are medically inoperable for tumor resection (due to confounding co-existing medical problems) are eligible without meeting any of the three minor criteria (a, b, or c).

Patients should be immediately threatened for vision loss or other significant neurological impairment directly related to tumor mass effect. As such, all patients enrolled would likely benefit from tumor response (shrinkage).

Patients with pituitary carcinomas are not eligible.

Number of patients = up to 12 in each or two cohorts listed below (total up to 24).

Patients will be divided into two cohorts depending on if they have been previously treated with radiotherapy or not.

Eligible patients may have a functioning or non-functioning adenoma and may have previously undergone a surgical resection for their adenoma.

The goal of the study is primarily to monitor for tumor shrinkage after seed implantation. Additional outcomes that will be monitored are change in visual fields, potential toxicities (acute and late) related to the treatment, progression free survival, and changes in patient reported outcomes.

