## 1.5 **Description of protocol therapy**

- 1.5.1 This study is a single arm Phase II pilot trial. Patients enrolled on the trial will undergo implantation of high activity iodine-125 seeds into their pituitary adenoma as outlined in sections 6 and 7. The tumor response to treatment will be monitored as well as change in visual fields, associated adverse effects, progression free survival and patient reported outcomes.

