6.9.3.2 Any adverse event equivalent to CTC V.4 grade 3, 4, or 5 or which precipitates hospitalization or prolongs an existing hospitalization must be reported regardless of designation (expected or unexpected) along with the attribution. This includes all deaths that occur within 30 days after the patient was discontinued from the study regardless of attribution AND any events that occur beyond 30 days and are considered probably related to treatment.

6.9.3.3 SAE reports must be completed (the CRF plus information describing the event, the grade, and the attribution) within 48 hours of the investigator's awareness of the occurrence of the event.

6.9.3.4 Attribution of an event can be categorized as:

- Not Related
- Possibly Related
- Probably Related
- Definitely Related

6.9.3.5 Adverse events (below grade 3) do not need to be submitted immediately. Rather, they should be documented in the Adverse Events Clinical Report Form (CRF) along with a brief description of the event, grade, and attribution).

All SAE reports should be made via FAX transmission to:

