11.3 Sample Size

11.3.1 **Overview:** The primary goal of this study is to monitor shrinkage in adenoma size and volume following treatment.

11.3.2 **Sample Size Derivation:** The predicted partial or complete response rate (PR+CR) of treated subjects at a follow-up interval of 12 months is the determinant of sample size. A PR + CR rate of 10% or less would be considered insufficiently low for further investigation of this treatment, whereas a PR + CR probability of 50% or higher will be considered worthy of future investigation. If the true PR + CR rate is 50%, a sample size of 10 patients will provide 87% power to detect a significantly higher RTS than 10% with an alpha level of 0.025. To assure an adequate number of evaluable patients, allowing for a small number of patients who would be lost to follow-up or otherwise found non evaluable, a total of up to 12 patients will be enrolled. This analysis applies to both cohorts (those with and without previous radiation therapy)

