11.4 Patient Accrual and Study Duration

11.4.1 It is expected that it will take approximately three to five years to complete the study. The analysis for tumor shrinkage will be carried out after each follow-up and collectively after each patient has had 365 days (i.e., 12 months) of follow-up. Study-related data will be stored for 5 years after termination of the study when accrual is no longer taking place and all patients have discontinued follow-up procedures. Blood drawn for translation research will be kept indefinitely or until exhausted.

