**12.2 Procedures**

- 12.2.1 Clinical trials are assessed for safety on a continual basis throughout the life of the trial. All SAE's and any AEs that are unexpected and possibly/likely related to study participation are reported to UTSW IRB through an electronic research system per UTSW IRB guidelines.
- 12.2.2 All clinical trials are reviewed on monthly basis for enrollment. All local SAEs are reviewed by Radiation Oncology DSMC monthly for severity and attribution. For investigator-initiated trials, all SAEs at affiliated institutions are monitored as local SAEs. The principle investigator and study coordinator will present a study treatment summary and SAEs for review. Source documents will be available for the DSMC members during the review. NCI Common Toxicity Criteria Version 4 will be used for grading and attributing adverse events.
- 12.2.3 If the SAE occurs on a multi-institutional clinical trial coordinated by the Radiation Oncology Clinical Research Office, the Clinical Research Manager or primary coordinator ensures that all participating sites are notified of the event and resulting action, within one (1) working day of the determination.
- 12.2.4 Interim Stopping Rules - Stopping for toxicity or efficacy will be related to dose limiting toxicity as described in the statistical section.

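### Do the undefined dose limiting toxicity and efficacy stop in 12.2.4 leave the 1/6 toxicity rule unworkable or its scope open?

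*Combined protocol and SAP*

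**What the plan says.** Section 12.2.4, in the data safety monitoring plan, reads: "Stopping for toxicity or efficacy will be related to dose limiting toxicity as described in the statistical section". Section 11 is the statistical section. Its one stopping rule is 11.3.3, which applies "If at any point during the study more than 1/6 of patients treated to date experience study treatment-related grade 4-5 toxicity of any kind"; enrollment to the study is then suspended. Possibly related events count as treatment-related.

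Three other places bear on scope and on efficacy:

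- Section 11.3.2 derives the sample size and adds "This analysis applies to both cohorts (those with and without previous radiation therapy". The cap is 12 patients per cohort and 24 in all.
- Section 1.5.1 states "This study is a single arm Phase II pilot trial".
- Section 11.4.1 states "The analysis for tumor shrinkage will be carried out after each follow-up", but attaches no decision to those analyses. Section 11.5.1.1 lists what interim reports generally contain: accrual, quality assurance and compliance, and toxicity.

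**The concern.** Two things look wrong. First, a safety committee member who follows 12.2.4 looks in Section 11 for a definition of dose limiting toxicity and for an efficacy stop, and finds neither. The sentence even makes an efficacy stop depend on toxicity, so it cannot be applied literally.

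Second, the cohorts are sized separately, yet 11.3.3 does not mention them. The denominator can change the decision. With 3 events in 12 patients of one cohort and none in 12 of the other, the pooled rate is 3/24 = 12.5%, within 1/6, while the cohort rate is 3/12 = 25%, above it. If the scope were really open, two people applying the trial's only toxicity limit could act differently on the same data.

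**Working it through.** **Reading the text.** Section 11.3.3 has three parts that could carry a scope. The trigger is any time in the study, the denominator is everyone treated so far, and the action is suspension of enrollment to the study. All three are at study level. The sentence just before the rule caps the whole study at 24. Where the authors wanted something to hold for each cohort they said so in 11.3.2, and they attached it to the sample size. No passage provides for suspending a single cohort.

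**Trigger points.** The plan gives no operating characteristics for the rule, so there is no stated figure to reproduce. Suspension requires 6x > n for x events in n patients: 1 event for n = 1-5, 2 for 6-11, 3 for 12-17, 4 for 18-23 and 5 at 24.

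**Assumptions for the size.** There are 12 patients per cohort, a common true rate p (with q = 1 − p), each outcome is known before the next patient enters, and suspension is final. The documents give no toxicity rate, so p = 5%, 10% and 15% are assumed.

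**Per-cohort denominator.** A cohort of 12 escapes suspension if it has no event in patients 1-5 and at most one in patients 6-11. After that, patient 12 cannot bring the count to 3. The probability is q⁵(q⁶ + 6pq⁵).

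- 5%: 0.7738 × (0.7351 + 0.2321) = 0.7484; at least one of two cohorts triggers with probability 1 − 0.7484² = 0.4399.
- 10%: 0.5905 × (0.5314 + 0.3543) = 0.5230; 1 − 0.5230² = 0.7265.
- 15%: 0.4437 × (0.3771 + 0.3993) = 0.3445; 1 − 0.3445² = 0.8813.

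**Study-wide denominator.** The same patient-by-patient recursion to n = 24 gives suspension probabilities of 0.2613, 0.5216 and 0.7321.

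**Difference, keeping the written action.** If 6(xA + xB) > nA + nB, then 6x > n in at least one cohort, so every study-wide trigger is also a cohort trigger. The probability that one reading suspends the study and the other never does is therefore a plain difference:

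| Assumed rate | Any cohort | Study-wide | Difference |
|---|---|---|---|
| 5% | 0.4399 | 0.2613 | 0.1786 |
| 10% | 0.7265 | 0.5216 | 0.2049 |
| 15% | 0.8813 | 0.7321 | 0.1492 |

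**Where the readings coincide.** An event in patients 1-5 of the study triggers both at the same patient. Its probability, 1 − q⁵, is 0.2262, 0.4095 and 0.5563. As a share of study-wide suspensions that is 0.2262/0.2613 = 87%, 0.4095/0.5216 = 79% and 0.5563/0.7321 = 76%.

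**Unequal rates.** With assumed rates of 1/3 and 10% and random entry order, the study-wide rule suspends in 0.9076 of trials. Per-cohort triggers occur with probability 0.9538 and 0.4770, so at least one occurs in 1 − 0.0462 × 0.5230 = 0.976. The study-wide rule still catches most of these trials.

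**The case for a change.** The best case for a change is that a stopping rule should have one meaning without inference. Reading dose limiting toxicity as the grade 4-5 criterion of 11.3.3 is an inference, and it leaves the efficacy words unexplained. The cohorts differ in prior radiotherapy and are sized separately, so a reader might expect a limit for each. If a cohort trigger suspended only that cohort, the readings would end with different cohorts suspended in 38%, 51% and 46% of trials at 5%, 10% and 15%. Two short wording edits would remove the question.

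Part of this stands. The terms in 12.2.4 do not match Section 11, and its efficacy words refer to nothing. The larger percentages do not stand, because they need a single-cohort suspension that the protocol never mentions. The concern about missed toxicity is also small. In the 1/3 and 10% case, the high-rate cohort is above 1/6 during accrual (six or more treated in it) and the study-wide rule never suspends in 5.3% of trials, or 13.4% if the other rate is 0%. The documents predict no toxicity difference between cohorts. Oversight does not rest on the limit alone: "SAE reports must be completed (the CRF plus information describing the event, the grade, and the attribution) within 48 hours" of the investigator becoming aware of the event, and "All local SAEs are reviewed by Radiation Oncology DSMC monthly for severity and attribution".

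**Conclusion.** No change to the plan is needed. The mismatch in 12.2.4 is a clerical slip in largely generic departmental text. The section it points to holds exactly one stopping rule, complete with grade, attribution, threshold and action, and nothing competes with it. The efficacy words have no effect: no boundary exists and the repeated shrinkage analyses carry no decision, so the trial simply runs to its planned size unless toxicity suspends it.

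On scope, 11.3.3 as worded is study-wide, and an analyst applying it literally reaches one workable limit. Writing that down would change no operating characteristic. The 18%, 20% and 15% differences measure what would turn on the other reading, under assumed rates, outcomes known at once and suspension treated as final. They are not evidence that the other reading was meant. A per-cohort limit would be a different design with its own cost: at equal rates of 5%, 10% and 15%, adding one from six patients in a cohort raises the chance of any suspension from 26% to 33%, from 52% to 64% and from 73% to 83%. That trade-off is the sponsor's to make, and the documents give no reason to press it.

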## **INTRODUCTION**

### **1.1 Epidemiology**

1.1.1 Pituitary adenomas constitute 10-20% of all central nervous system tumors. Patients with secretory adenomas most frequently present with endocrinopathies; the goal of therapy in these cases is normalizing the endocrinopathy and eliminating further lesion growth. First-line therapy can be either medical or surgical depending on the hormone being secreted. Thirty percent of pituitary adenomas are nonsecretory and present clinically due to their progressive increase in size and the mass effect exerted on the surrounding tissues, most commonly, the optic apparatus. Controlling tumor growth and preserving vision are the most important factors in the treatment of nonsecreting adenomas. Surgery is considered first-line treatment for these tumors.

Tumors with their greatest diameter of less than 10mm are classified as “microadenoma”, whereas those with a diameter of 10mm or more are considered “macroadenomas”. Due to their benign nature and variable clinical presentation, pituitary adenomas may become very large, a factor that complicates treatment. Widespread surgical and radiologic interest in these tumors has resulted in various definitions of pan-invasive or “giant” pituitary adenomas. Both Fisher et al. and Symon et al. defined giant adenomas as those showing suprasellar extension of more than 40 mm in any direction from the midline of the jugum sphenoidale. Symon et al. also considered giant adenomas to be tumors extending within 6 mm of the foramen of Monro. Others considered adenomas with suprasellar extension of Hardy grades C and D as being large or giant. Mohr et al. felt that having a superior margin more than 20 mm above the jugum sphenoidale was the key to identifying giant adenomas. More recently, Goel et al. defined giant adenomas as those with greater than 4 cm in maximum diameter, further subclassifying them into four grades according to invasion and patterns of extension. Despite definitional variations, all of the authors agree that very large tumors are difficult to treat by surgery alone and that adjuvant therapy is necessary.

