### **1.4 Rationale and preliminary evidence for protocol therapy**

1.4.1 Given the need to treat patients with pan-invasive macroadenomas that were experiencing worsening symptoms secondary to mass effect on surrounding tissues and who have previously underwent surgical resection with recurrence of disease or who were not candidates for surgical intervention, an alternative intervention was sought to decompress the adenoma and prevent further deteriorating symptoms or to possibly improve their symptoms.

Previous experience in the treatment of meningiomas with brachytherapy using permanent interstitial implantation of high activity iodine-125 (I-125) seeds provided the impetus for this current protocol. Kumar et al. treated 13 patients with interstitial high activity I-125 seeds. Indications for implantation included recurrence after initial surgery or as a primary modality of treatment in patient who were not candidates for surgery. All 13 patients were alive at a median follow up of 25 months. Nine of the 13 patients achieved complete resolution of the tumor, while in the remaining four, more than 50% reduction in tumor volume was noted. The striking finding of this study was the time-frame in which tumor response was observed. The minimum time to achieve complete response was 3 months. Additionally, no acute or late complications secondary to this technique of brachytherapy was observed. Given these promising results, we

sought to apply a similar technique for the treatment of pan-invasive pituitary macroadenomas that required rapid decompression in order to prevent further deterioration of symptoms.

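### From the sixth patient on, one treatment-related death does not by itself suspend enrolment, because section 11.3.3 gives it the same weight as a single grade 4 event

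*Combined protocol and SAP*

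**What the plan says.** Section 11.3.3 introduces the rule with "There will be an early stopping rule for unexpected toxicity" and sets the trigger: if "more than 1/6 of patients treated to date experience study treatment-related grade 4-5 toxicity of any kind, study enrollment will be suspended". The test is continuous and uses a running denominator: "If at any point during the study more than 1/6 of patients treated to date". Attribution is broad: "Treatment related events include those related or possibly related to therapy". The text just above the rule caps enrolment: "The sample size of this study will not exceed 24 patients". The rule is written for all treated patients together, with no version for each cohort.

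Section 12.2.4 (interim stopping) sets no threshold of its own. It refers to dose-limiting toxicity as described in the statistical section, but that section defines no such toxicity. Section 11.3.3 is therefore the only rule that can be applied.

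Other oversight exists. Section 6.9.3.2 requires grade 3-5 events to be reported, and 6.9.3.3 sets 48 hours for serious adverse event reports. Section 12.2.2 states that "All local SAEs are reviewed by Radiation Oncology DSMC monthly for severity and attribution", with the principal investigator presenting the events. Section 12.2.3 has participating sites told of an event and the action taken within one working day of the determination.

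**The concern.** The rule looks only at how many patients have a grade 4-5 event, not at which grade it is. A patient who dies from the implant procedure or the radiation adds one to the numerator, exactly as a patient with a single grade 4 event does. Because the threshold is strict (more than 1/6), the first such death passes once 6 patients have been treated.

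That fits poorly with the trial's own premise. Section 1.1 describes the disease in these words: "Due to their benign nature and variable clinical presentation, pituitary adenomas may become very large". Section 1.4 supports the implant with a 13-patient meningioma series in which "no acute or late complications secondary to this technique of brachytherapy was observed". Against that background a related death is the kind of unexpected toxicity the rule is meant to catch. If the plan is followed as written, further patients can receive a permanent implant after such a death without anyone being required to decide that this is acceptable.

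**Working it through.** **Inputs.** From 11.3.3: suspend if k/n > 1/6, where k is the number of treated patients with a related or possibly related grade 4-5 event and n is the number treated to date. Maximum n is 24. The plan gives no operating characteristics for the rule, so there is no figure to reproduce, and it gives no expected death rate. The rates below are assumptions, shown as a range.

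**Step 1: what the threshold allows.** Enrolment stays open while 6k ≤ n.

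| Patients treated | Most events without suspension | Check |
|---|---|---|
| 1-5 | 0 | 1/5 = 0.200 > 0.1667, suspends |
| 6-11 | 1 | 1/6 is not more than 1/6 |
| 12-17 | 2 | 2/12 = 1/6 |
| 18-23 | 3 | 3/18 = 1/6; 4/23 = 0.174 suspends |
| 24 | 4 | 4/24 = 1/6, but enrolment is complete |

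While enrolment is open the ceiling is therefore 3, and that requires spacing: the first event at or after 6 treated, the second at or after 12, the third at or after 18. Of the 8,855 ways to place 4 events among the first 23 patients, none passes.

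**Step 2: how often a death passes.** Only the first 23 patients are used, because a suspension after patient 24 protects nobody from enrolment. Assume each patient has a related death with probability r, deaths become known in treatment order before the next patient is treated, and there are no grade 4 events. Let w(n,k) be the probability of k deaths after n patients with no suspension so far, starting from w(0,0) = 1. Then

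w(n,k) = (1 − r)·w(n−1,k) + r·w(n−1,k−1) if 6k ≤ n, and 0 otherwise.

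The probability of at least one death and no suspension is the sum of w(23,k) over k ≥ 1. Under these assumptions only deaths can suspend, so it also equals 1 − (1 − r)^23 minus the probability of suspension. For r = 5%: 1 − 0.95^23 = 69.3%, suspension 26.1%, difference 43.1% (from unrounded values).

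| Assumed death rate r | At least one death | Suspended | At least one death, no suspension | Two or more deaths, no suspension |
|---|---|---|---|---|
| 1% | 20.6% | 5.1% | 15.6% | 1.2% |
| 2% | 37.2% | 10.2% | 27.0% | 3.9% |
| 5% | 69.3% | 26.1% | 43.1% | 14.0% |
| 10% | 91.1% | 52.2% | 39.0% | 21.3% |

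The fourth column falls between 5% and 10% because at the higher rate the rule fires more often.

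**Step 3: sensitivity to grade 4 events.** Each related grade 4 event uses up the same allowance. Let a patient have a death with probability 5%, a grade 4 event without death with probability g, or neither, and run the same recursion. The chance of at least one death and no suspension falls from 43.1% (g = 0) to 25.6% (g = 5%) and 12.9% (g = 10%).

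**Step 4: sensitivity to timing.** If a death becomes known only after more patients have been treated, n is larger and the death passes more easily. The tables do not include this effect, which works in the opposite direction to step 3.

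**The case against.** The strongest reply is that the gap is narrower than it looks and that people, not only a ratio, watch this trial. Several parts of that reply stand.

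- The rule is strict early on: any related or possibly related death among the first 5 treated suspends at once.
- A reader might infer from 4/24 = 1/6 that four deaths could pass without stopping enrolment. The rule does not allow this. It runs continuously and 4/23 exceeds 1/6, so a fourth death passes only when all 24 patients are treated and no enrolment is left to suspend.
- A reader might also infer that deaths go unexamined. Sections 6.9.3 and 12.2 require prompt reporting and monthly review, and 12.2.3 presupposes that some determination is made. If accrual of 24 patients filled the expected three to five years, it would average 24/60 = 0.4 to 24/36 = 0.67 patients a month, so monthly review is not slow relative to enrolment.
- The death rates are assumed. At low rates, and with any grade 4 events, the probabilities are well below 43.1%, and most of that figure is a single death.
- Although the tumour is benign, patients must face an immediate threat to vision or neurological function (3.1.4), and section 1.5 region of the rationale itself acknowledges many complications with early pituitary implants. Some risk is foreseen.

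What the reply does not supply is a sentence that links a related death to a pause, or to a recorded decision to go on. Review for severity and attribution is not the same thing, and the committee's freedom to act is not a requirement to act.

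**Conclusion.** The point holds as a gap in the design. The documents do not contradict themselves here, and the rule can be operated. With no other grade 4-5 events, up to 3 related deaths could occur while enrolment is open without suspending it, and from the sixth treated patient one death alone never does.

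The arithmetic of the threshold needs no assumption beyond the wording of 11.3.3. The probabilities do: they rest on assumed death rates of 1% to 10%, events in treatment order, and no grade 4 events. On the last point they are upper figures, while late-emerging deaths would raise them. They show that the gap is not a remote edge case; they do not predict this trial's death rate. The change is cheap and worth making.

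**What to change.** Keep the 1/6 rule and add to 11.3.3:

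> In addition, any grade 5 event related or possibly related to study treatment (implant procedure or radiation) suspends enrolment until the DSMC has reviewed it and recorded a decision to continue.

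This governs enrolment only. It leaves dose, schedule, sample size and patient care unchanged, and it uses the committee and the attribution wording that the plan already has. The cost is an occasional pause, sometimes for a death later judged unrelated. At a true 1% rate of such deaths, the chance of at least one pause in 24 patients is 1 − 0.99^24 = 21%, and each pause ends when the committee records its decision.
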